10.1. Safety Variables

10.1.1. Safety

Safety data will be collected as in section 9.0. Safety will be monitored continuously by the study investigators for every subject through day 90 following the last dose of study therapy or until 30 days post-surgery, whichever happens first. Safety data will be collected and stored in CRMS. A detailed statistical analysis plan for safety including stopping rules is contained in section 11 of this protocol.

10.1.2. Feasibility

The feasibility of neoadjuvant immunoradiation will be based on subjects proceeding to surgery without extended treatment-related delays. A treatment related delay will be considered "extended" if it is greater than 8 weeks (56 days) following the initially planned surgery date. For feasibility, a drug-related toxicity of any grade, that in the judgment of the investigator or surgeon could adversely impact perioperative morbidity or mortality, should delay the planned operative date.

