Patients with a history of prior thoracic radiation or interstitial lung disease/pneumonitis will be excluded. Patients who would require a pneumonectomy will be excluded. This study aims to determine if immunoradiation will be safe, tolerable and feasible to administer prior to surgical resection for patients with stage III NSCLC. Safety will be determined by the number of dose-limiting toxicities that delay the time to surgery by >8 weeks from the date of completion of thoracic RT, and pre-defined grade 3+ pulmonary toxicities that occur during the DLT observation period in comparison to historic norms of pulmonary toxicities seen with chemoradiation prior to surgery . Feasibility will be defined as the number of patients who undergo surgery within the planned surgical window: 6-8 weeks after completion of thoracic RT. The DLT observation window will start from the day of commencement of immunotherapy, until 30 days after thoracic surgery or 100 days after the last dose of immunotherapy, whichever is longer.

From a translational perspective, this study will allow investigators to collect pre- and post-treatment tumor and lymph node tissue and serial blood and related biospecimens, aimed at examining potential mediators of response and resistance to immunoradiation. Other endpoints of clinical interest will include: pathologic response, radiologic response, recurrence-free survival (RFS), overall survival (OS) and surgical morbidity and mortality. Patients will undergo routine screening investigations including CBC, CMP, Hepatitis B/C/HIV assessment, urine, pregnancy test, and standard radiologic body imaging and brain imaging at least 28 days prior to enrollment. Patients will be monitored with a clinical visit with a study doctor, AE assessment and routine laboratory tests (CBC, CMP, endocrine labs) at each week of thoracic RT and dose of immunotherapy and at a pre-surgical and post-surgical visits. After completion of study therapy, patients will be followed every 12 weeks (+/-7 days) for 12 months with standard radiologic imaging, laboratory tests and an AE assessment, and then every 12 weeks (+/-7 days) for years 2 and 3 to assess survival status.

of Patients (planned):

Cohort 1: Identify 20 eligible and evaluable subjects, enroll 16 subjects. Cohort 2: Identify 20 eligible and evaluable subjects, enroll 16 subjects.

Inclusion Criteria:

- Written informed consent and any locally-required authorization obtained.

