3.1.4. Treatment and Collection of Biological Specimens

Sixteen patients with resectable IIIA NSCLC (squamous and non-squamous) will receive preoperative durvalumab on days 1, 30 and 60, (week 1, 4, 8), concurrently with thoracic radiation weeks 1-5 (+/-2) before planned surgery on 6-8 weeks after completion of thoracic radiation. Thoracic radiation will be performed as part of standard of care, to a total of 45Gy in 25 fractions using standard radiation methods employed at the Sidney Kimmel Comprehensive Cancer Center at Johns Hopkins University. Serial peripheral blood samples for exploratory analyses will be collected prior to each dose of study drug(s), once within 3 days prior to surgery, and at a timepoint 30 days (+/- 7 days) after surgery, as detailed in Figure 1. Preoperative core biopsy of the primary tumor, and optional preoperative mediastinal lymph node biopsies, will be

18 Nov 2020 Page **56** of **164**

obtained. Archived or new tissue specimens will fulfill these criteria. Details of sample requirements are detailed in section 8.3. Specific procedures for accessioning specimens are outlined in detail in the laboratory manual. Patients will have one tumor imaging of the chest during the 7 days prior to surgery to re-assess tumor status and potential pulmonary inflammation following neoadjuvant treatment. Surgery for patients enrolled on this protocol will be according to generally accepted standards of care. It is advised that patients have at least 3 mediastinal and hilar lymph node stations sampled during surgery. The treatment plan is outlined in section 6.0

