6.2. Dosage and Administration

6.2.1. Durvalumab monotherapy or Durvalumab and Tremelimumab

Dosage of study therapy to be administered in this protocol is outlined below in Table 2.

In cohort 1: Three doses of durvalumab monotherapy will be administered to enrolled patients on Days 1, 30 and 60 (+/- 3 days) concurrently with standard thoracic radiation from day 1 until days 25-28, prior to planned surgery. Thoracic surgery will take place 6-8 weeks after completion of thoracic radiation.

In cohort 2: Three doses of durvalumab + tremelimumab will be administered to enrolled patients on Days 1, 30 and 60 (+/- 3 days) concurrently with standard thoracic radiation from day 1 until day 25-28 prior to planned surgery. Thoracic surgery will take place 6-8 weeks after completion of thoracic radiation.

Dosing of study therapy is flat dosing.

TABLE 2: TRIAL TREATMENT

Drug	Dose/Potency*	Dose Frequency	Route of Administration	Regimen/Treatment Period	Use
Durvalumab	1500 mg	Q4W	IV infusion	Day 1 of each 4 week cycle	Experimental
Tremelimumab	75mg	Q4W	IV infusion	Day 1 of each 4 week cycle	Experimental
(cohort 2 only)					

18 Nov 2020 Page **73** of **164**

The rationale for dosing is outlined in sections 1.0 and 5.0. Trial treatment should begin on the day of registration or as close as possible to the date on which treatment is allocated/assigned. Refer to Section 5.0 for the administration and monitoring of administration of durvalumab and tremelimumab.

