12.1. Study Design

This is an open-label pilot study aimed at establishing the safety and feasibility of neoadjuvant immunoradiation prior to surgical resection of stage III NSCLC, that is deemed surgically resectable by a thoracic surgeon with lobectomy. Thoracic RT will be given at standard doses and fractionation to a total dose of 45Gy in 25 fractions, as per published phase III data⁴⁹, and using standard methods. In cohort 1, the safety and feasibility of durvalumab with concurrent thoracic RT, will be assessed. In this cohort, durvalumab will be administered at the standard dose of 1500mg IV every 4 weeks for 3 doses, as per ongoing phase III studies. If preliminary safety is established in cohort 1, the study will expand to include cohort 2, which will test the safety and feasibility of durvalumab plus tremelimumab with concurrent thoracic RT. In this cohort, durvalumab will be administered at the standard dose of 1500mg IV every 4 weeks for 3 doses, and tremelimumab will be administered at the standard dose of 75mg every 4 weeks for 3 doses. The primary endpoints of this study are safety and feasibility in cohort 1 and cohort 2 (if applicable). Patients will be observed for perioperative grade 3-4 adverse events through day 90 following the last dose of immunotherapy or until 30 days post-surgery, whichever is longer. Safety and feasibility will be monitored continuously throughout the study through weekly meetings with investigators, as well as the planned Bayesian monitoring rules (see below). A set of markers of immune reactivity measured in lung tumor resection specimens, draining lymph nodes, and peripheral blood will be evaluated. Feasibility will be evaluated as the proportion of evaluable patients who successfully complete preoperative treatment and proceed to surgery without any extended treatment related delays. Extended treatment-related delay will be defined as >8 weeks from the day of completion of thoracic RT. For each cohort, we aim to accrue 16 evaluable patients, defined as those who receive at least one dose of durvalumab or durvalumab/tremelimumab administration and have complete toxicity follow-up. We plan to accrue 20 patients to ensure 16 evaluable patients are available for analysis. If less than 16 evaluable patients are available after accruing 20 patients, we will amend the protocol to ensure at least 16 evaluable patients are available for analysis.

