12.2. Study Endpoints Definition

12.2.1. Primary Endpoints

Safety of durvalumab monothererapy (cohort 1) +/- durvalumab+tremelimumab (cohort 2) administered preoperatively together with thoracic radiation in stage III NSCLC.

Safety will be measured by the frequency of any of the following events:

• Drug-related adverse events occurring up to 100 days after the last dose of immunotherapy or 30 days after surgery (whichever is longer).

18-Nov-2020 Page **114** of **164**

- Serious adverse events occurring up to 100 days after the last dose of immunotherapy or 30 days after surgery (whichever is longer).
- Clinical laboratory test by worst toxicity grade (as assessed at the time intervals outlined in the Schedule of Assessments, Figure 1.)

Feasibility of preoperative administration of durvalumab monothererapy (cohort 1) +/- durvalumab+tremelimumab (cohort 2) concurrently with thoracic radiation in stage III NSCLC

Feasibility will be evaluated through the proportion of evaluable patients who successfully complete preoperative treatment and proceed to surgery without any extended treatment-related delays defined as >8 weeks from the last day of thoracic radiation.

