12.2.3. Feasibility Endpoint

Stopping guideline for feasibility

The feasibility of neoadjuvant durvalumab monotherapy (cohort 1) or durvalumab+tremelimumab (cohort 2) together with thoracic radiation prior to surgery will be based on the proportion of evaluable patients proceeding to surgery without extended treatment-related delays. A treatment-related delay will be considered "extended" if it is greater than 8 weeks following completion of thoracic radiation. For feasibility, drug-related toxicity of any grade, that in the judgment of the investigator or surgeon could adversely impact perioperative morbidity or mortality, should delay the planned operative date.

We would consider the experimental regimen is "infeasible" if the probability of not proceeding to surgery as planned is convincingly (more than 70%) more than .25, i.e., the probability of proceeding to surgery as planned is convincingly less than 75%. We assume about 10% of patients will have their surgery delayed and there is about 14% chance that the risk will be 25% or more. This corresponds to a Beta (0.1,0.9) prior distribution. Table 10.5 summarizes the continuous stopping rule for the 16 evaluable patients for each regimen. The feasibility stopping rule calls for the study to be paused for a review if the number of patients successfully proceeding to surgery is too low, starting from the 6th evaluable patient.

Table 10.5 Stopping Rule for Feasibility

# patients with delay in planned surgery	3	4	5	6
Out of total # evaluable patients	6-7	8-10	11-14	15-16

Table 10.6 summarizes the operating characteristics based on 5,000 simulations with 16 evaluable patients in terms of how frequent the study would stop based on the stopping rule under different hypothetical feasibility rates, as well as the average sample sizes.

Table 10.6 Operating characteristics of the stopping rule for feasibility

Underlying feasibility	0.65	0.7	0.75	0.8
% of time study stops	37.9%	13.9%	6.4%	2.1%

18-Nov-2020 Page **117** of **164**

Expected sample size	13.8	15.2	15.6	15.9

If the feasibility stopping boundary is reached, we will re-evaluate the clinical advantages of the treatment, pathological tumor response and prolonged RFS, against the risks and consider re-designing the regimen to allow more time between the last dose of immunotherapy and surgery to better manage potential side effects.

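### Section 10.1.2 sets the co-primary feasibility limit 6 to 8 weeks later than Section 12 does; the feasibility threshold, DLT window and stopping-rule event also differ between passages

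*Combined protocol and SAP*

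**What the plan says.** **Feasibility limit.** Section 10.1.2 calls a treatment-related delay extended "if it is greater than 8 weeks (56 days) following the initially planned surgery date". Section 12.1 states: "Extended treatment-related delay will be defined as >8 weeks from the day of completion of thoracic RT". The primary endpoint in 12.2.1 is the proportion of evaluable patients who complete preoperative treatment and "proceed to surgery without any extended treatment-related delays defined as >8 weeks from the last day of thoracic radiation". The feasibility stopping rule in 12.2.3 counts a delay as extended "if it is greater than 8 weeks following completion of thoracic radiation". The planned date comes from 3.1.4 ("thoracic radiation weeks 1-5 (+/-2) before planned surgery on 6-8 weeks after completion of thoracic radiation") and 6.2.1 ("Thoracic surgery will take place 6-8 weeks after completion of thoracic radiation").

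**Feasibility event in the synopsis.** The Methodology paragraph says: "Feasibility will be defined as the number of patients who undergo surgery within the planned surgical window: 6-8 weeks after completion of thoracic RT". That counts surgery inside the window whatever the cause of delay. The feasibility entry under Safety Assessments counts DLTs that push surgery beyond 8 weeks after radiation. The Statistical methods paragraph combines surgery in the window with absence of treatment-related delays.

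**Feasibility threshold.** The synopsis suspends accrual at a posterior probability of at least 90% that fewer than 75% of patients proceed. Section 12.2.3 uses more than 70%.

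**DLT window.** Section 6.3 and the synopsis run to the later of 100 days after the last dose and 30 days after surgery. The AE and SAE endpoints in 12.2.1 use the same window. Sections 3.1.5, 12.1 and 12.2.2 (the stopping rule) use 90 days in place of 100. Sections 10.1.1 and 14.2, on monitoring, use 90 days or 30 days after surgery, whichever comes first.

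**Safety event.** Section 12.2.2 first refers to adverse events of interest and points to Section 9.2. It then refers to grade 3-4 toxicities of the types in 6.3. Table 10.1 counts DLTs. The synopsis Methodology paragraph says: "Safety will be determined by the number of dose-limiting toxicities that delay the time to surgery by >8 weeks", and adds pre-defined pulmonary toxicities of grade 3 or higher.

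**The concern.** Feasibility and safety are the co-primary endpoints, and each drives a Bayesian rule that can suspend accrual in a cohort of 16. Each needs one event, one time limit and one threshold. As written, two people applying different sections to the same patient could classify that patient differently. With so few patients, one reclassification can move a count across a boundary. It also moves the reported proportion by 1/16 = 6.25 percentage points. Cohort 2 opens once the safety and feasibility of cohort 1 are established (Figure 2), so the classification bears on that step as well.

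**Working it through.** **1. The plan's own figures reproduce.**
- Feasibility prior Beta(0.1, 0.9): P(rate > 0.25) = 0.142. Section 12.2.3 says about 14%.
- Safety prior Beta(0.05, 0.95): P(rate > 0.25) = 0.070. Section 12.2.2 says about 7%.
- The safety rule (70% posterior threshold, looks from patient 3 to 16) gives exact stopping probabilities of 16.3, 29.3, 44.3, 59.4 and 72.8% at true risks of 0.15 to 0.35. Table 10.2 has 15.8, 29.3, 43.1, 60 and 72.8%.

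**2. Both feasibility limits on one time scale.** Inputs: planned surgery 6 to 8 weeks after radiation (3.1.4, 6.2.1), plus 8 weeks in 10.1.2.
- 10.1.2: 6 + 8 = 14 to 8 + 8 = 16 weeks after radiation (98 to 112 days).
- Section 12: 8 weeks after radiation (56 days).
- Difference: 6 to 8 weeks (42 to 56 days).

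In study days, 25 fractions at 5 per week starting on day 1 end on day 33. Planned surgery is then day 33 + 42 = 75 to 33 + 56 = 89. The Section 12 limit is day 89. The 10.1.2 limit is day 75 + 56 = 131 to 89 + 56 = 145.

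Treatment-related delays are classified as follows:

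| Surgery, weeks after radiation | Section 12 | Section 10.1.2 |
|---|---|---|
| 8 | not extended | not extended |
| 10 | extended | not extended |
| 12 | extended | not extended |
| more than 16 | extended | extended |

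**3. What one patient does to the feasibility rule.** With r delays in n patients, the posterior is Beta(0.1 + r, 0.9 + n - r). The rule compares P(delay rate > 0.25) with the threshold. The synopsis states no prior, so the 12.2.3 prior is used for both thresholds.

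| Delays in 6 | P(rate > 0.25) | 70% (12.2.3) | 90% (synopsis) |
|---|---|---|---|
| 2 | 0.570 | continue | continue |
| 3 | 0.851 | suspend | continue |
| 4 | 0.969 | suspend | suspend |

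Moving from two delays to three suspends accrual under 12.2.3, as the first column of Table 10.5 shows. It does not under the synopsis threshold.

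**4. The safety rule.** With the safety prior, 1 DLT in 4 patients gives 0.339 and 2 in 4 gives 0.755. One DLT counted or not counted can therefore cross the 70% threshold.

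**5. The DLT window.** For last dose on day L and surgery on day s:

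gap = max(L + 100, s + 30) - max(L + 90, s + 30).

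The gap is 10 days if s is at most L + 60, and zero if s is at least L + 70.
- Three doses (L = 60): 10 days for surgery up to day 120, 5 days at day 125, zero from day 130.
- Two doses (L = 30): 10 days for surgery up to day 90, zero from day 100.
- One dose (L = 1): zero from day 71.

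**6. The safety event.** Section 9.2 covers severity grading and causality and lists no events, so the pointer leads nowhere. Section 6.3 includes grade 2 pneumonitis that has not resolved to grade 1 or lower within 3 days of starting maximal supportive care. The grade 3-4 wording, read literally, leaves that event out, while Table 10.1 counts DLTs without qualification. The documents give no rate for it, so the number of DLTs affected cannot be computed.

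**The case against.** The strongest reply is that the governing feasibility definition is clear. The endpoint, design and stopping-rule texts in Section 12 agree, the synopsis shares the 8-week upper limit, and 10.1.2 is a single outlier. That is largely right, and it is why the remedy is simple. It does not remove the conflict: 10.1.2 is the protocol's own section on the feasibility variable, uses a different starting point and spells out the 56 days.

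It is also fair that no distribution of surgical delays is given, so the number of patients who would be reclassified is unknown, and that one patient matters at the boundary of any 16-patient rule.

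Several stronger readings are tempting but not supported:
- **One extra delay always decides suspension.** At three in six this holds only at the 70% threshold.
- **Every patient loses 10 days of DLT observation.** The gap depends on the last dose and the surgery date, and can be zero after one or two doses.
- **DLTs would be counted only to 30 days after surgery.** The shorter period in 10.1.1 and 14.2, which ends at the earlier of the two dates, describes safety monitoring, not DLT counting.
- **The Figure 1 visit weeks settle which limit was meant.** Those visits are timed to planned surgery, which is the same under either limit.
- **Safety data are lost.** Section 9.3.1 records adverse events through follow-up, and a crossed boundary leads to suspension and review, not automatic termination.

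On the safety event, it can be argued that calling grade 3-4 toxicities the primary DLTs of concern need not exclude the grade 2 pneumonitis item. That is a possible reading, but the text should not leave the choice open.

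**Conclusion.** The point stands. The co-primary feasibility endpoint has two incompatible limits, 8 weeks against 14 to 16 weeks after radiation. The 14 to 16 weeks is derived from the planned surgery window and is not printed in 10.1.2. Treatment-related delays that fall between the two limits change classification. The feasibility rule has two posterior thresholds, and they disagree at three delays in six (85%, assuming the 12.2.3 prior applies to both).

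The DLT window conflict is real but secondary: at most 10 days, shrinking to zero with later surgery or fewer doses, and small in effect. The safety-event wording needs one definition, but its numerical effect cannot be determined. The feasibility definition must be corrected because it decides who counts in a co-primary endpoint and in a rule that suspends accrual.

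**What to change.** 1. Replace the delay sentence in 10.1.2 with the 12.2.1 endpoint definition. Use that one feasibility event in the synopsis Methodology, Safety Assessments and Statistical methods paragraphs.
2. In the same edit, choose one posterior threshold for the feasibility rule, 70% or 90%, state it in both the synopsis and 12.2.3, and make the stopping tables match it.
3. Reconcile 3.1.5, 6.3, 10.1.1, 12.1, 12.2.1, 12.2.2, 14.2 and the synopsis so that the DLT definition, its window and the event counted in Table 10.1 are the same. Because a DLT ends study treatment under 6.3, the choice of window and definition belongs to the sponsor and investigators.
4. Correct the Section 9.2 pointer in 12.2.2.

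**Cost.** These are text edits with no new visits. If the threshold changes, the feasibility boundaries and operating characteristics must be recalculated. If the reconciled window is the 100-day one, complete toxicity follow-up, and with it the review after six patients, comes up to 10 days later.

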10.1.3. Surgical Morbidity and Mortality

[figure not shown]
Adverse events of any grade that occur in the postoperative period (day of surgery until 30 days post surgery), will be collected. These data will be obtained by weekly review of the subject's medical record by study investigators. The attributions of these AEs will also be recorded, as per section 9.3. Deaths that occur in the postoperative period will be recorded, and the attribution of any subject death will be recorded.

18-Nov-2020 Page **111** of **164**

10.2. Efficacy Variables

10.2.1. Pathologic Response

In patients who proceed to surgical resection, pathologic response in resection specimens will be evaluated by two thoracic pathologists, and stratified into major pathologic response (MPR: 90% reduction in tumor cells), partial response (PR: 10-90% reduction) and no response (NR:0-10% reduction), as per published methods^{61, 62} (Figure 3). The rate of MPR, PR and NR will be recorded. Pathologic responses will

be correlated with clinical outcomes, including RFS. In the neoadjuvant study of single agent anti-PD-1 in patients with early stage (stage IB-IIIA (N1) NSCLC discussed earlier by [name] et al, approximately ~50% of patients exhibited major pathologic responses in resection specimens (MPR: >90% reduction in tumor cells). We anticipate that the same number of patients or greater will exhibit MPRs, to the combination of anti-PD-L1+/-CTLA-4 together with thoracic radiation, in this study.

